Safety is an important first step and study outcome. In the published phase 2 and 3 studies of solriamfetol in patients with narcolepsy or obstructive sleep apnea (OSA), adverse events included headache (9-16%), nausea (12-14%), diarrhea (11%), decreased appetite (6-14%), anxiety (6-11%), chest discomfort (9%), insomnia (6%), muscle tightness (6%), nasopharyngitis (5-14%), and dry mouth (5-10%). Cancer patients and in particular brain tumor patients are at risk for some of these and other cognitive, seizure, or neurological toxicities that need to be explored at each of solriamfetol's three dose levels (75 mg, 150 mg, 300 mg) prior to proceeding to a primary efficacy endpoint. The current trial will establish this experience.

Prior studies of solriamfetol have shown early improvements in patient-reported sleep by ESS scores. In the current study we will also evaluate other associated symptoms of fatigue, neurocognition, mood, and quality of life. It is not clear that these associated symptoms will respond as quickly to drug therapy. In fact, according to our model of the sleep-fatigue-neurocognitive symptom cluster (Figure 1), we suspect that improvement in fatigue, neurocognition, mood and quality of life are downstream of the improvement in sleep and thus, in this study, endpoints will be assessed after prolonged stable drug therapy. This should not affect the ability to assess for improvements in sleep which have been reported as early as 1 week after solriamfetol treatment and remained stable over up to 12 weeks of continued treatment in the aforementioned studies.

2 Hypotheses

1. Primary Hypothesis

We hypothesize that the side effect profile of solriamfetol at doses of 75 mg daily, 150 mg daily, and 300 mg daily will be similar in patients with primary brain tumors to that reported in patients with narcolepsy and obstructive sleep apnea.

Serious adverse events in patients with primary brain tumors including significant confusion/ altered mental status, seizures, or other side effects will not be more common at the 300 mg daily dose compared to the 150 mg and 75 mg daily doses.

2. Secondary Hypotheses

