Secondary hypotheses include that solriamfetol treatment at maximal patient specific dosing will result in improvements in patient-reported excessive daytime sleepiness and sleep quality (e.g. ESS and PSQI), neurocognitive function (see below for neurocognitive battery), fatigue and mood (e.g. Brief Fatigue Inventory, Cancer Fatigue Scale, Beck Depression Inventory), and quality of life (FACT-Brain).

3. Exploratory Hypotheses

Improvements in objective measures of sleep (e.g. actigraphy, sleep diary) will be similar to those reported in prior studies (e.g. obstructive sleep apnea, narcolepsy). We hypothesize that improvements in sleep, neurocognition, fatigue, mood, and quality of life may vary by clinical factors such as corticosteroid use, antiepileptic use, and tumor grade by World Health Organization (WHO) classification.

3 Objectives

1. Primary Objective(s)

1. To estimate the safety of solriamfetol at 75 mg daily, 150 mg daily, 300 mg daily as assessed by NCI CTC Adverse Events (v5.0) in patients with primary gliomas compared to prior studies⁴⁵⁻⁴⁷

2. Secondary Objective(s)

1. To estimate the effect of solriamfetol on sleep by Epworth Sleepiness Scores (ESS) scores in patients with primary gliomas and compare the effect to previously published scores in patients with OSA
2. To estimate the effect of solriamfetol on sleep quality by Pittsburgh Sleep Quality Index scores
3. To estimate the effect of solriamfetol on neurocognitive function based on a disease-specific neurocognitive battery (see neurocognitive battery below)
4. To estimate the effect of solriamfetol on patient-reported fatigue (Brief Fatigue Inventory, Cancer Fatigue Scale) & mood (Beck's Depression Inventory)
5. To estimate the effect of solriamfetol on patient-reported QOL (FACT-Br)
6. To estimate the effect of solriamfetol on objective sleep-wake times by actigraphy and sleep diary (pre- vs post-treatment)

3. Exploratory Objective(s)

1. To explore a biologic gradient effect of increasing doses of solriamfetol on actigraphy
2. To explore differences in clinical activity of solriamfetol by corticosteroid use, antiepileptic use, and tumor grade

4 Patient Selection

Inclusion and exclusion criteria represent standard criteria for other sleep studies in this population (e.g. inclusion criteria) and standard exclusions for prior studies of this agent (e.g. exclusion criteria).^{8,39,40}

1. Inclusion Criteria

1. WHO Grade 2-4 infiltrating glioma by histologic confirmation

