This is a single-arm, open label, non-randomized safety study in patients with glioma with each patient undergoing both a dose-escalation and fixed drug continuation phase of the study. The primary objective is to compare the safety of oral solriamfetol at doses of 75 mg daily, 150 mg daily and 300 mg daily. Secondary objectives include determining the effect of solriamfetol on patient-reported sleep, neurocognition, fatigue, mood, quality of life, and objective measures of sleep.

1. Primary Outcome

1. The primary outcome measure will be adverse events as assessed by the NCI Common Terminology Criteria for Adverse Events (CTCAE) version 5.0.

2. Secondary Outcomes

1. The effect of solriamfetol on patient-reported sleep will be assessed by Epworth Sleepiness Scale (ESS) scores
2. The effect of solriamfetol on patient-reported sleep quality will be assessed by Pittsburgh Sleep Quality Index (PSQI) scores.
3. The effect of solriamfetol on neurocognitive function will be assessed by a disease-specific Neurocognitive Battery (Section 7.8).
4. The effect of solriamfetol on patient-reported associated symptoms will be assessed by the Brief Fatigue Inventory (BFI) and the Cancer Fatigue Scale (CFS) for determining the effect on fatigue and by the Beck's Depression Inventory (BDI) for determining the effect on depression and mood.
5. The effect of solriamfetol on patient-reported QOL will be assessed by the FACT-Brain module (FACT-Br).
6. The effect of solriamfetol on changes in objective sleep-wake times will be assessed by actigraphy and patient-reported sleep diary (see Section 7.8).

3. Exploratory Outcomes

1. Actigraphy in relation to increasing doses of solriamfetol.
2. Differences in clinical activity of solriamfetol by treatment factors will be assessed by recording corticosteroid dose at baseline, antiepileptic use (presence/absence of prescribed antiepileptic and dose at baseline), and tumor grade by World Health Organization (WHO) criteria.

7 Treatment Plan

1. Overview of Treatment Plan

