This is a single-arm, open label, two-part safety study of solriamfetol in patients with WHO grade 2-4 gliomas. Patients with stable disease by clinical examination and neuroimaging who have an ESS \geq 10 and meet all inclusion/exclusion criteria will be recruited and enrolled. First, all patients will receive solriamfetol at escalating doses. Second, all patients will complete a fixed dose drug continuation treatment at the patient-specific maximum tolerated dose.

The study will occur in 3 phases:

Open Label Safety Study of Solriamfetol to Promote Wakefulness and Improve Cognition and Quality of Life in
Patients with Primary Gliomas
Wake Forest Baptist Comprehensive Cancer Center
WFBCCC 98418

1. Pre-Treatment Baseline (~1 week)
2. Flexible Dose Titration (~3 weeks)
3. Fixed Dose Drug Continuation (~6 weeks)

Patients will initially complete a 1-week baseline actigraphy and sleep diary prior to treatment initiation to establish a baseline sleep pattern.

Solriamfetol will be dosed by flexible dose titration starting at 75 mg daily in all patients and escalating after 7 days (1 week) to 150 mg daily and then after 7 days to 300 mg daily for a total duration of 3 weeks (flexible dose titration period). Patients who experience a dose-limiting toxicity will be de-escalated to the last tolerated dose level and move to the fixed dose drug continuation phase. Prior studies incorporating this design have used a 3-day treatment prior to escalation.⁴⁹ For this study, 7 days has been selected to provide a sufficient period of time to observe both immediate and delayed toxicities that could be seen in this population.

Following completion of the flexible dose titration, patients will continue solriamfetol at 300 mg daily or their maximally tolerated dose for a treatment duration of 6 weeks. For this period of the study, 8 weeks has been selected to allow for time to observe both short term improvement in patient-reported sleep as well as potentially more delayed changes in other study endpoints (i.e. fatigue, mood, neurocognition).

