Storage Requirements: solriamfetol tablets are to be stored at room-temperature conditions, 15°C to 30°C (59°F to 86°F).

Stability: Studies are ongoing to monitor the stability of solriamfetol tablets.

12 Data Management

Informed consent document	EPIC
Protocol registration form	OnCore
Adverse Events Log (Appendix E)	OnCore
Patient Drug Diary (Appendix F)	
Fixed Dose Patient Drug Diary (Appendix G)	
Epworth Sleepiness Scale (Appendix H)	
Pittsburgh Sleep Quality Index (Appendix I)	
Brief Fatigue Inventory (Appendix J)	
Cancer Fatigue Scale (Appendix K)	
Beck's Depression Inventory (Appendix L)	
Neurocognitive Battery Form (Appendix M)	
FACT-Br (Appendix N)	
Concurrent Medication (Appendix O)	OnCore
Off-Study Form (Appendix P)	OnCore
MR Imaging Record (Appendix Q)	
Sleep Diary and Actigraphy Record (Appendix R)	
Glioma History (Appendix S)	

13 Statistical Considerations

This is a single-arm, open label, non-randomized safety study in patients with stable glioma disease. The primary outcome is safety of oral solriamfetol as doses of 75 mg daily, 150 mg daily and 300 mg daily. Secondary outcomes include ESS score, PSQI score, a composite neurocognitive battery score, FSS score, BDI score, and FACT-Br score.

1. Analysis of Primary Objective

For the primary outcome, NCI Common Terminology Criteria for Adverse Events (CTCAE) version 5.0 will be used for scoring toxicity and adverse events.

The severity and frequency of toxicity and adverse events for each dose of solriamfetol will be tabulated using descriptive statistics. The proportions of subjects who experienced grade 3 or above toxicities will be estimated, along with 95% confidence intervals by each type of toxicity.

To compare the safety of solriamfetol at 75 mg daily, 150 mg daily, 300 mg daily, chi-squared statistics will be used. If there are some cells with expected value <5 , Fisher's exact test will be used for the comparison.

2. Analysis of Secondary Objective

For the secondary outcomes, descriptive statistics will be performed for each of the outcome measures. Changes in pre- and post-treatment scores will be assessed and compared using the pair-t tests if the changes follow a normal distribution and using the Wilcoxon signed rank tests if the changes do not follow a normal distribution. For the comparison between the change in ESS score in the study patients and the published change score in patients with obstructive sleep apnea, we will use the one sample t-test for this comparison.

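### Section 13.1 compares 75, 150 and 300 mg with independent-groups tests although one nested cohort takes the doses in turn, and it does not say which exposure period counts for each dose

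*Combined protocol and SAP*

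**What the plan says.** Section 13.1 (Analysis of Primary Objective) sets two tasks. The first is a table: "The severity and frequency of toxicity and adverse events for each dose of solriamfetol will be tabulated using descriptive statistics". The second is a test: "To compare the safety of solriamfetol at 75 mg daily, 150 mg daily, 300 mg daily, chi-squared statistics will be used", replaced by Fisher's exact test when an expected count is below 5.

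The design is one arm with dose escalation within each patient. Section 7.1 says: "First, all patients will receive solriamfetol at escalating doses". After titration, "patients will continue solriamfetol at 300 mg daily or their maximally tolerated dose for a treatment duration of 6 weeks". Section 13.4 expects 36 patients at 75 mg, at least 33 at 150 mg and at least 30 at 300 mg, all from the same 36.

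The primary objective is worded in two ways. Section 6 says: "The primary objective is to compare the safety of oral solriamfetol at doses of 75 mg daily, 150 mg daily and 300 mg daily". Section 3.1 instead aims to estimate safety "in patients with primary gliomas compared to prior studies". Section 2.1 adds the hypothesis that serious events "will not be more common at the 300 mg daily dose compared to the 150 mg and 75 mg daily doses". Section 13.4 powers only a combined-dose comparison and describes the study as mainly descriptive.

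No section names a within-patient method for AEs. Section 13.2 does use paired tests, but for the secondary scores.

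**The concern.** Two things are missing from Section 13.1.

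- **Independence.** Each patient reaching 300 mg also contributes to the 75 and 150 mg columns. Chi-squared and Fisher's test treat those columns as different people. The error they attach to a dose difference is then wrong, and the direction matters for a hypothesis that events are not more common at the top dose.
- **The period that counts.** A table by dose needs a rule for events that persist across an escalation, start after a dose reduction, or occur in the fixed phase or the 30-day follow-up. Section 13.1 gives none. The telephone script (Appendix T) and the one-week drug diary (Appendix F) point to the titration weeks, and the interim safety analysis (Section 13.7) falls at the end of escalation, but Section 13.1 adopts none of these. The fixed-phase diary (Appendix G) prints a single dose, 300 mg, although Sections 7.1 and 7.6 allow a lower patient-specific dose.

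The second gap affects the descriptive tables as well as the p-value. Two analysts could both follow Section 13.1 and report different primary tables.

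**Working it through.** **Inputs.** Group sizes 36/33/30 and alpha 0.10 come from Section 13.4; Section 13.1 states no alpha, so 0.10 is borrowed. The AE rates of 10% to 20% are also from Section 13.4. The phase rates of 48.9% (titration) and 10.2% (stable dose), each over 2 weeks, come from the randomized-withdrawal trial in Section 1.5.2. The within-patient correlation phi is not in the documents; 0.22 and 0.40 are assumed.

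**1. The plan's own figure.** Section 13.4 gives detectable proportions of 24% and 36% against 10% and 20%. A one-sample exact binomial test with n = 36 and 0.10 in the upper tail reproduces them. Rejecting at 7 or more events has size 0.063 and 79.5% power at 24%; rejecting at 11 or more has size 0.089 and 80.2% power at 36%. This is a comparison with prior rates. No stated figure supports the between-dose test.

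**2. Pairing, equal periods.** For 300 mg against 75 mg with a common risk p, and leaving unrelated to AEs:

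- variance assumed by the test: p(1−p)(1/36 + 1/30) = 0.0611 p(1−p)
- actual variance: p(1−p)(1/36 + 1/30 − 2·phi/36) = 0.0489 p(1−p) at phi 0.22, and 0.0389 p(1−p) at phi 0.40

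The assumed variance is too large by a factor of 1.25 or 1.57. Simulation of the full planned rule at 20% for every dose (random-intercept logistic model) gives rejection of about 6% and 2.5% instead of 10%.

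Power falls accordingly. With true rates 20/28/36% and phi about 0.30, the three-group chi-squared has 29% power, against 41% for Cochran's Q in the 30 patients with all three doses. Q's own null size is 9.8% at 20% per dose and a similar phi. At 3% per dose the planned rule rejects 4.9% / 3.3%. Sparse counts already hold it below nominal, so pairing matters little for rare events.

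**3. Length of exposure.** Titration starts on D8 and steps up on D15 and D22, so 75 and 150 mg have 7 days each. For 300 mg the period is:

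- 7 days if it ends on D29
- up to 14 days if it ends at the clinic visit on D29+7 (D36 − D22)
- 49 days if the 6-week fixed phase counts (7 + 42)

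A dose reduction adds 7 days at the lower dose (Section 7.9.1).

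**4. Fixed phase counted at 300 mg, no dose effect.**

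- Weekly titration risk: 1 − √(1 − 0.489) = 28.5%.
- Later hazard: −ln(1 − 0.102)/2 = 0.0538 per week.
- 300 mg column: 1 − (1 − 0.285)·exp(−6 × 0.0538) = 48.2%.

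The columns read 28.5/28.5/48.2%. Exact enumeration of all 36/33/30 tables with independent records gives rejection of 51% at alpha 0.10 and 37% at 0.05. With within-patient correlation the 0.10 figure is 48% / 46%.

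**5. Titration only, 20% per week.** If every 300 mg period ran 14 days, that column would read 1 − 0.8² = 36%, and the test would reject 43% with independent records or 40% / 36% with correlation. With an 8-day period it rejects 11%.

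**6. Persisting events.** Suppose six patients have an AE that starts at 75 mg and continues.

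- Counted at every dose (6/36, 6/33, 6/30), the smallest expected count is 18 × 30/99 = 5.5, so chi-squared applies: p = 0.94.
- Counted at onset only (6/36, 0/33, 0/30), the smallest expected count is 6 × 30/99 = 1.8, so Fisher's test applies: p = 0.003.

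**The case against.** The case for leaving the plan alone has real substance.

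- The study is mainly descriptive, and only the combined-dose comparison is powered. That stands: pairing does not touch that comparison or the estimation aim in Section 3.1. It does not excuse the missing period, because per-dose descriptive tables depend on it.
- A reader might infer that ignoring pairing inflates false positives. It does not. With equal periods the test is conservative, and for the rare serious events in Section 2.1 the effect is small.
- A reader might infer that the plan counts fixed-phase events at 300 mg. Section 13.1 does not say so, and Appendices F and T point the other way. The 51% shows what the wording permits, not what will happen. Likewise D29+7 is a visit allowance, and not every 300 mg period would run 14 days.
- A reader might conclude that the chi-squared/Fisher rule should be deleted. Section 13.3.2 takes its method from Section 13.1 for groups defined by corticosteroid use, antiepileptic use and tumor grade. Those groups contain different patients, so the rule suits binary outcomes there.
- A ban on Cochran's Q or McNemar would go too far. With six leavers, all chosen AE-first, Q rejects 24% / 20% under the null. With one leaver at each step it rejects 12% / 12%. Only dose-limiting toxicities stop escalation, so the first pair is a worst case. A mixed logistic model has slightly liberal size (about 11% to 12%), so its apparent power gain is not size-matched.

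**Conclusion.** The point holds and should be fixed. As written, Section 13.1 applies tests for independent groups to nested records and leaves the dose period undefined.

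The pairing error is moderate and in the conservative direction: about 6% or 2.5% actual size at a nominal 10%, with lost power for a dose gradient. It rests on the assumed phi and the borrowed alpha. The undefined period is the larger matter. Under one permitted reading, unequal exposure alone would make 300 mg look worse and give rejection of 51% (37% at 0.05). That assumes AE rates in sleep apnea patients, titrated in 3-day steps, carry over to glioma patients.

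The documents do not support a claim that the trial's overall safety assessment is invalid.

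**What to change.** In Section 13.1:

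- (a) Assign each AE by onset date to the dose being taken. Limit the between-dose comparison to the first period at each titration dose, and report days of exposure per dose.
- (b) Tabulate fixed-phase and follow-up AEs separately, by dose taken and with exposure time.
- (c) For the between-dose comparison only, replace chi-squared/Fisher with per-dose proportions, exact confidence intervals and within-patient differences. If a p-value is wanted for common AE types, use a within-patient method, preferably one that uses all records, such as a mixed logistic model. Note that completers-only tests can be biased when escalation stops for toxicity. For sparse and serious events give counts and exact intervals only; 0/30 has a 95% upper limit of 1 − 0.025^(1/30) = 11.6%.
- (d) State that dose is confounded with order, time and tolerance of earlier doses.

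Elsewhere:

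- (e) Write the chi-squared/Fisher rule into Section 13.3.2 for binary outcomes across corticosteroid, antiepileptic and grade groups.
- (f) Reconcile the single dose field in Appendix G with Sections 7.1 and 7.6.

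The cost is SAP wording and slightly more analysis, with no added patients or visits. Rule (a) needs AE onset dates; the content of the AE log (Appendix E) is not visible here, so whether it already records them cannot be judged. The downside is that continuation-phase events leave the between-dose comparison, which then captures only early events.
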